5.3 Primary outcome

The primary outcome will be analysed using a mixed-effect logistic regression model, with a random intercept for centre [9]. The model will be adjusted for the minimisation variables as fixed factors [10], which are country, planned use of epidural anaesthesia, and planned surgical category as follows: (a) resection of colon, rectum or small bowel; (b) resection of liver, pancreas or gall bladder; (c) resection of stomach (non-obesity surgery); (d) resection of oesophagus (non-obesity surgery); (e) Obesity surgery; or (f) vascular procedure; (g) Other intra-peritoneal surgery. For the minimisation variable planned surgical procedure, any category from (a)-(f) with fewer than 15 patients will be combined with other intra-peritoneal surgery. The model will also be adjusted for the following pre-specified baseline covariates [11-13]: age, gender (M/F), at least one co-morbid disease (chronic respiratory disease, ischaemic heart disease, diabetes mellitus, heart failure, liver cirrhosis, active cancer, and previous stroke or transient ischaemic attack), smoking status (current smoker) and ASA score (I & II

vs. III & IV). All covariates will be included in the model as fixed factors. Age will be included as a continuous variable, assuming a linear association with the outcome [14]. Categorical covariates with more than two categories (country, planned surgical category, ASA score) will be included using indicator variables. The magnitude of the treatment effect will be reported as an adjusted odds ratio with a 95% confidence interval. Missing data for baseline covariates will be handled using mean imputation for age, and a missing indicator will be added for missing data for categorical variables (gender, co-morbid disease, smoking status, and ASA score) [15].

5.4 Secondary outcomes

Secondary outcomes will be analysed using the same approach as the primary outcome (i.e. a mixedeffect logistic regression model, with a random intercept for centre), except they will adjust only for the minimisation variables apart from country (i.e. the model will be adjusted only for planned use of epidural anaesthesia and planned surgical category). This is to avoid over-stratification, as the expected event rate for these outcomes is low. This analysis strategy will be used for the following secondary outcomes:

- 1. Pneumonia within 30 days of randomisation
- 2. Endotracheal re-intubation within 30 days of randomisation
- 3. All-cause mortality within 30 days of randomisation
- 4. Post-operative infection within 30 days of randomisation.
- 5. Postoperative mechanical ventilation (invasive or non-invasive) within 30 days of randomisation.
- 6. All-cause mortality at one year after randomisation

5.5 Process measures

Summary measures will be presented separately for each treatment group. All patients with recorded data will be included in the summary. Formal statistical analysis will not be performed. Re-admission to hospital within 30 days of randomisation will be summarised by number (%). Days in critical care will be summarised for the subset of patients admitted to a critical care unit using mean (SD) and median (IQR). Duration of hospital stay will be summarised using mean (SD) and median (IQR).

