3.3 Process measures

In addition, we will use the following process measures (i.e. non-patient centred outcome measures), to facilitate comparison with other research:

- Re-admission to hospital within 30 days of randomisation
- Days in critical care (defined as either level 2 or level 3 critical care)
- Duration of hospital stay (days)

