5.7 Graphs and other data summaries

- The flow of study participants will be displayed in Consolidated Standards of Reporting Trials (CONSORT) diagram.
- 30-day and one-year survival of patients will be presented for both groups using Kaplan-Meier survival curves.
- Investigator self-assessment of blinding by treatment allocation will be presented as number (%).
- Duration of level 2 and 3 critical care stay within 30 days of randomisation for patients admitted to a critical care unit will be presented as mean (SD) and median (IQR).
- Data describing a predefined list of the most common post-operative complications occurring within 30 days of randomisation will be collected for all patients.

The number and percentage of patients experiencing each of the following complications will be presented by (a) treatment allocation; (b) treatment allocation and Clavien-Dindo (CD) grade (I-II vs III-V); and (c) treatment allocation and CPAP delivery method for those in the CPAP group only. These summaries will not be subjected to any statistical testing. These complications are:

Respiratory complications:

- o Pneumonia
- o Pleural effusion
- o Pneumothorax
- o Bronchospasm
- Aspiration pneumonitis
- Acute Respiratory Distress Syndrome (ARDS)

Infective complications:

- Surgical site infection (superficial)
- Surgical site infection (deep)
- Surgical site infection (organ space)
- Urinary tract infection
- Infection, source uncertain
- Laboratory confirmed blood stream infection

Cardiac complications:

- Myocardial infraction
- o Arrhythmia
- Cardiogenic pulmonary oedema
- o Cardiac arrest with successful resuscitation

Other complications:

- Acute kidney injury
- Pulmonary embolism
- o Stroke
- Acute psychosis or delirium
- o Bowel infarction
- o Anastomotic leak
- Perforation of viscus (e.g. bowel, gall bladder etc.)
- Postoperative haemorrhage
- Other postoperative haemorrhage
- Any other complication

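### Critical care days are summarised by arm only among admitted patients, so the printed figures do not compare the randomised groups; an all-randomised row would fix this cheaply

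*SAP*

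**What the plan says.** Section 3.3 of the SAP lists days in critical care (level 2 or level 3) as a process measure, included "to facilitate comparison with other research". Section 5.5 then sets the rules:

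- By arm: "Summary measures will be presented separately for each treatment group".
- General population for process measures: "All patients with recorded data will be included in the summary".
- Exception for this measure: "Days in critical care will be summarised for the subset of patients admitted to a critical care unit", as mean (SD) and median (IQR).
- No test: "Formal statistical analysis will not be performed".

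Section 5.7 adds, by level of care, "Duration of level 2 and 3 critical care stay within 30 days of randomisation for patients admitted to a critical care unit". Tables 9 and 10 in Appendix 2 carry a footnote limiting the summary to admitted patients. The first row of Table 10 is the number and percentage admitted in each arm. No planned summary gives a non-admitted patient 0 days.

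**The concern.** Under section 4.2 patients are randomised up to four hours after the end of surgery, and under section 4.1 allocation is open. Admission to critical care therefore generally comes after allocation and may be influenced by it. Section 4.3 itself treats intensive care admission as a stand-in for re-intubation, a component of the outcome that CPAP is meant to reduce. If CPAP changes who is admitted, the admitted patients in the two arms are selected differently, and a difference in their mean stay mixes that selection with any change in length of stay.

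Section 5.11 recognises the general problem when it weights the per-protocol set to allow for exclusions made after randomisation. What is at stake here is narrower: a reader who takes the by-arm durations as a measure of critical care use could read a saving where use has risen, or the reverse.

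**Working it through.** The SAP states no critical care admission rate or length of stay, so there is no plan figure to reproduce. All inputs below are assumptions chosen to show direction.

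**Relation.** Let p be the share admitted in an arm and m the mean days among those admitted. With the non-admitted counted as 0,

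mean days per randomised patient = p × m.

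The plan prints m by arm. The randomised comparison is of p × m.

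**Single illustration.** Usual care: p = 0.30, m = 3. CPAP: the same stays, plus a further 0.10 of patients admitted for 1 day each.

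- Among admitted: usual care 3.0; CPAP (0.30 × 3 + 0.10 × 1) / 0.40 = 1.00 / 0.40 = 2.5.
- Per randomised patient: usual care 0.30 × 3 = 0.90; CPAP 0.30 × 3 + 0.10 × 1 = 1.00.

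The admitted-only figure falls by 0.5 days while use rises by 0.10 days per patient.

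**Range.** Stays last 1 day (short) or 6 days (long). Usual care admission is 20%, 40% or 60%, with 50% or 70% of admissions short. Two changes under CPAP are tried: a quarter of short admissions averted, or 5 percentage points of 1-day admissions added. Each cell gives days among admitted / days per randomised patient.

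| Admitted, usual care | Short share | Usual care | Short stays averted | Short stays added |
|---|---|---|---|---|
| 20% | 50% | 3.50 / 0.700 | 3.86 / 0.675 | 3.00 / 0.750 |
| 20% | 70% | 2.50 / 0.500 | 2.82 / 0.465 | 2.20 / 0.550 |
| 40% | 50% | 3.50 / 1.400 | 3.86 / 1.350 | 3.22 / 1.450 |
| 40% | 70% | 2.50 / 1.000 | 2.82 / 0.930 | 2.33 / 1.050 |
| 60% | 50% | 3.50 / 2.100 | 3.86 / 2.025 | 3.31 / 2.150 |
| 60% | 70% | 2.50 / 1.500 | 2.82 / 1.395 | 2.38 / 1.550 |

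Worked example, 40% admitted and 50% short. Usual care: 0.20 × 1 + 0.20 × 6 = 1.40, and 1.40 / 0.40 = 3.50. Averted: 0.15 × 1 + 0.20 × 6 = 1.35, and 1.35 / 0.35 = 3.86. Added: 0.25 × 1 + 0.20 × 6 = 1.45, and 1.45 / 0.45 = 3.22.

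The two measures move in opposite directions in all 12 comparisons. That follows from the design of the cases: adding or averting stays shorter than m always has this effect. If CPAP instead averted 5 points of 6-day stays from the single illustration, days would be 0.90 − 0.05 × 6 = 0.60 per patient and 0.60 / 0.25 = 2.4 among admitted. Both would then fall. Reversal is possible, not inevitable.

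**What a reader can recover.** With s the SD among admitted, the all-patient variance is p × s² + p(1 − p) × m². Check on the worked usual care arm: m = 3.5 and s² = 6.25, so 0.40 × 6.25 + 0.40 × 0.60 × 12.25 = 2.50 + 2.94 = 5.44. Directly: 0.20 × 1 + 0.20 × 36 − 1.40² = 7.40 − 1.96 = 5.44. The all-patient median is 0 whenever fewer than half are admitted. The upper quartile, and the median when half or more are admitted, cannot generally be recovered from the printed summaries.

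**The case against.** The strongest reply is that the plan claims no effect here. The measure is descriptive, with no estimate, interval or test, and the section 5.11 warning concerns a treatment-effect analysis rather than a table. The safeguards against misreading are also largely in place: Table 10 puts the number admitted by arm directly above the durations, both tables footnote the restriction, and Table 2 shows planned and actual level of care on the first night. In the single illustration a reader would see 30% against 40% admitted beside the durations and could work out the rise. Some admissions are planned before surgery, which limits how far allocation can move them. Most of this stands, and it is why the point is minor.

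It does not remove the point. The durations are still set out by arm, for use in comparison with other research, and the reader must do the multiplication. That also requires the count and the days to cover the same window: Table 10 uses 30 days, while section 5.5 names no window for days in critical care.

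Three stronger readings are tempting but not supported:

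- Section 5.5 might seem to contradict itself by including all patients with recorded data and then a subset. It states a general rule and then a specific exception, which section 5.7 and the tables follow.
- The all-patient figures might seem lost. The mean and SD are recoverable, and the median is known to be 0 if fewer than half are admitted.
- The planned table might seem bound to mislead. The documents give no admission rates or stay lengths, and the cases above vary short stays only.

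**Conclusion.** The point holds as a minor, inexpensive improvement. The by-arm critical care durations describe subsets formed largely after open allocation. They are not a comparison of the randomised groups and can point opposite to total critical care use. In the assumed range the admitted-only mean moved by 0.12 to 0.50 days one way while days per randomised patient moved by 0.025 to 0.105 the other. These sizes rest wholly on the assumed admission shares and on the change being confined to short stays; the actual size and direction cannot be derived from the SAP. A reader might infer that the trial's conclusions are at risk. They are not: the measure is an untested process measure outside the primary and secondary outcomes.

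**What to change.** - In section 5.5 and Table 9, add a row for critical care days over all randomised patients with recorded data, with non-admitted patients counted as 0 days. Give mean (SD) as well as median (IQR), because the median may be 0.
- In section 5.7 and Table 10, add the same row for level 2 and for level 3 days.
- Keep the admitted-only rows and the existing count of patients admitted. Extend the footnote to say that the admitted-only figures are descriptive and not a randomised comparison.

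The cost is a few words of SAP text and the extra table rows. No new data are needed, and no other analysis changes.

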5.6 Safety outcome measures

Each safety outcome measured will be summarised for patients in the CPAP group by the number (%). All patients with a recorded outcome will be included in the summary. In addition to this, 'other'

adverse events will be reported separately if prevalence is more than 1% across all participants in the trial.

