3.4 Safety outcome measures

Safety outcomes will quantify harm associated with CPAP (appendix). Presence or absence of the following pre-defined adverse events will be measured within 24 hours of the end of surgery in patients in the treatment group only:

- Interface intolerance due to excessive air leaks
- Pain
- Cutaneous pressure sore or pressure area
- Claustrophobia
- Oro-nasal dryness
- Hypercapnia
- Haemodynamic instability
- Vomiting
- Aspiration of gastric contents
- Other harm assessed as probably or definitely related to CPAP

4. Study Methods

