4.2 Randomisation

Randomisation will occur after the participant has provided informed consent and up to four hours after the end of surgery. Participants will be centrally allocated to treatment groups (1:1) by a computer-generated dynamic procedure (minimisation) with a random component. Minimisation variables will be country, surgical procedure category and planned use of epidural anaesthesia. The surgical procedure categories are as follows: (a) resection of colon, rectum or small bowel; (b) resection of liver, pancreas or gall bladder; (c) resection of stomach (non-obesity surgery); (d) resection of oesophagus (non-obesity surgery); (e) obesity surgery; (f) vascular procedure; or (g) other intra-peritoneal surgery. Each participant will be allocated with 80% probability to the group that minimises between group differences in these factors among all participants recruited to the trial to date, and to the alternative group with 20% probability. To enter a patient into the PRISM trial, research staff at the site will log on to a secure web-based randomisation and data entry platform and complete the patient's details to obtain a unique patient identification number and allocation to a treatment group.

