5.2.2 Comparability of groups

Baseline demographic and clinical data for patients randomised to CPAP (treatment group) and usual care (usual care group) will be summarised but not subjected to statistical testing. Numbers (%) and means (SD) or medians (IQR) will be provided separately for each group. The treatment and usual care groups will be compared at entry for the following baseline characteristics:

- Demographic: age (years), gender (male/female)
- Co-morbid disease: (a) COPD; (b) asthma; (c) interstitial lung disease or pulmonary fibrosis; (d) bronchiectasis; (e) ischaemic heart disease; (f) diabetes mellitus; (g) heart failure; (h) liver cirrhosis; (i) active cancer; (j) previous stoke or TIA; (k) respiratory infections within the previous month; (I) HIV
- Current smoker
- ASA grade: I; II; III; IV

- Body mass index (kg/m^2)
- Minimisation criteria:
 - Planned surgical procedure: (a) resection of colon, rectum or small bowel; (b) resection of liver, pancreas or gall bladder; (c) resection of stomach (non-obesity surgery); (d) resection of oesophagus (non-obesity surgery); (e) obesity surgery; (f) vascular surgery; (g) other intra-peritoneal surgery
 - Country: (a) Italy; (b) Spain; (c) Sweden; (d) United Kingdom; (e) South Africa; (f) Norway
 - Planned use of epidural
- Surgical procedure performed: (a) Resection of colon, rectum or small bowel; (b) resection of liver, pancreas or gall bladder; (c) resection of stomach (non-obesity surgery); (d) resection of oesophagus (non-obesity surgery); (e) obesity surgery; (f) vascular procedure; (g) other intraperitoneal surgery
- Pre-operative blood tests results: (a) haemoglobin (g/dL); (b) creatinine (μmol/L)
- ARISCAT score: ARISCAT is a risk index based on seven patient factors that evaluates risk for postoperative pulmonary complications in a patient [7, 8]. The seven factors are used to calculate this score are: age, oxygen saturation measured by pulse oximetry (SpO₂, %), pre-operative haemoglobin concentration, respiratory infection in the last month (yes/no), surgical incision category (peripheral/abdominal/thoracic), duration of surgery (hours) and emergency procedure (yes/no). ARISCAT score will be calculated for both groups and presented in the baseline data table. The component variables will be tabulated separately for reference. The ARISCAT Score and its individual components will only be summarised for patients who have all components of the score complete.

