Gastro-intestinal bleed											
Other postoperative haemorrhage											
Any other complication											

Table 9: Process measures

included in		Summary measure	
Usual Care (n=XXXX)	CPAP (n=XXXX)	Usual Care	СРАР
	Usual Care	Care (n=XXXX)	(%) Usual Care (n=XXXX) Usual Care

Abbreviation: SD, standard deviation; IQR, interquartile range.

^aSummarised only for patients admitted to critical care unit

Table 10: Critical care stay within 30 days of randomisation ^a

Critical Care Stay within 30 days of randomisation		ients included in s - no. (%)	Summary measure	
	Usual Care (n=XXXX)	CPAP (n=XXXX)	Usual Care	СРАР
Number of patients admitted to a critical care unit - no. (%)				
Duration of level 2 critical care stay (days)				
Mean (SD)				
Median (IQR)				
Duration of level 3 critical care stay (days)				
Mean (SD)				
Median (IQR)				

Abbreviation: SD, standard deviation; IQR, interquartile range.

^aSummarised only for patients admitted to critical care unit

Table 11: Summary of CPAP for patients randomised to the CPAP group

CPAP Characteristics	Number of patients included in analysis - no. (%)	Summary measure
	CPAP (n=XXXX)	СРАР
Number of patients who received CPAP - no. (%)		
Total duration of CPAP within 12 hours of the end of surgery (minutes)		
Mean (SD)		
Median (IQR)		
Maximum airway pressure received within 12 hours of the end of surgery		
(cmH ₂ O)		
Mean (SD)		
Median (IQR)		
Primary method of CPAP delivery - no. (%)		
Face mask		
Helmet device		
Nasal mask		
Extra research staff present to help deliver CPAP - no. (%)		
Staff administering CPAP used equipment to monitor airway pressures - no. (%)		
Staff administering CPAP used equipment to monitor FiO2 - no. (%)		
Patient had a nasogastric tube in situ during CPAP - no. (%)		

Abbreviation: IQR, interquartile range; SD, standard deviation; CPAP, continuous positive airway pressure

Table 12: Safety outcome measures

Adverse Events - no.(%)	CPAP (n=XXXX)
Patients with ≥ 1 adverse event	XX (XX.X %)
Total number of adverse events	XXX
Number of adverse events per patient	
0	XXX (XX.X %)
1	XXX (XX.X %)
2	XXX (XX.X %)
3	XXX (XX.X %)
4	XXX (XX.X %)
Type of adverse event	
Interface intolerance due to excessive air leak	XXX (XX.X %)
Pain	XXX (XX.X %)
Cutaneous pressure area	XXX (XX.X %)
Claustrophobia	XXX (XX.X %)
Oronasal dryness	XXX (XX.X %)
Hypercapnia	XXX (XX.X %)
Haemodynamic instability	XXX (XX.X %)
Vomiting	XXX (XX.X %)
Aspiration of gastric contents	XXX (XX.X %)
Other	XXX (XX.X%)

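### The CPAP adverse event tables use everyone randomised to CPAP with a recorded outcome as the denominator, not those who received CPAP, which can dilute device-specific rates (minor)

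*SAP*

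**What the plan says.** Section 3.4 gives the purpose: "Safety outcomes will quantify harm associated with CPAP". The listed events "will be measured within 24 hours of the end of surgery in patients in the treatment group only", as present or absent.

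Section 5.6 gives the summary: "Each safety outcome measured will be summarised for patients in the CPAP group by the number" and percentage. The only condition on who is counted follows: "All patients with a recorded outcome will be included in the summary". Section 5.2.2 shows what the group labels mean: "patients randomised to CPAP (treatment group) and usual care (usual care group"). Tables 12 and 13 have a single CPAP column with no mention of receipt.

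Elsewhere the SAP separates recipients from non-recipients. Failure to give CPAP is the first deviation in section 5.2.5 and has its own row in Table 3. Section 5.11 excludes CPAP-group patients given no CPAP from the per-protocol efficacy analysis. The first row of Table 11 is "Number of patients who received CPAP - no". and percentage.

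On timing, section 4.2 allows randomisation "up to four hours after the end of surgery".

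**The concern.** A table meant to describe the harm of a device should have as its denominator the people exposed to the device. Several listed events need that exposure. Intolerance from air leaks cannot occur without an interface, and claustrophobia or a pressure sore is of interest here because of the mask or helmet. Unexposed patients entered as event-free add to the denominator and nothing to the numerator.

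The plan makes this separation for efficacy, where it is a secondary analysis, but not for harm, where exposure matters more. A clinician or patient reading Table 12 wants the risk to someone given CPAP. The printed percentage may be that risk multiplied by the share who received it.

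Timing is a second, weaker issue. The observation window opens at the end of surgery, so for some patients it can include time before randomisation and before CPAP. Pain, vomiting and haemodynamic instability are common to recovery from surgery. Safety is measured in one arm only, so there is no usual care rate against which to judge the background.

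**Working it through.** **Inputs**
- CPAP group size: 2400 planned (section 4.3), used only to turn percentages into counts. It agrees with the plan's own assumptions. For 11.7% against 8.8% at 90% power and two-sided 5%, the usual two-proportion formula gives 2297 per group; 2297 / 0.96 = 2393 after 4% loss, or 4786 in total against the stated 4800.
- Share of the CPAP group receiving none, *q*: not given in the SAP. Assumed 5%, 10% and 15%.
- Rate of a device-specific event among recipients, *r*: not given. Assumed 10%.
- The SAP states no expected safety rate, so there is no safety figure to reproduce.

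**Denominator**

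Let *s* be the share of non-recipients whose safety items are recorded as absent rather than left blank. For an event that cannot occur without CPAP:

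printed rate = *r*(1 − *q*) / [(1 − *q*) + *s q*]

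If *s* = 0 (all blank), the printed rate is *r* and there is no dilution. If *s* = 1 (all recorded as absent), it is *r*(1 − *q*), and the relative understatement equals *q*. For *s* = 1:

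| *q* | Recipients of 2400 | Events at 10% | Printed, events / 2400 | Among recipients |
|---|---|---|---|---|
| 5% | 2280 | 228 | 9.5% | 10% |
| 10% | 2160 | 216 | 9.0% | 10% |
| 15% | 2040 | 204 | 8.5% | 10% |

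The SAP does not say which value of *s* applies.

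The formula does not carry over to non-specific events. A patient given no CPAP can still vomit or have pain, so non-recipients may add to the numerator too.

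**Window**

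The window runs 24 hours from the end of surgery, and randomisation may be as late as 4 hours into it: 4 / 24 = 17% of the window. This is the most that can precede randomisation, and it is a share of time, not of events. For a patient randomised at or before the end of surgery it is zero. Any gap between randomisation and the start of CPAP comes on top. The SAP gives no rate for events before CPAP, so no event count follows. Counting such events would raise non-specific rates while dilution lowers rates, so the net effect on those rows cannot be signed.

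**The case against.** The strongest reply is that the decisive step is not in the document. Section 5.6 counts only patients with a recorded outcome. If the case report form leaves these items blank when no CPAP was given, the denominator is already close to recipients. This stands, and it is why the size above is conditional. It does not remove the point, because the SAP does not say so and stating the denominator would settle it.

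It can also be said that summarising by allocated group follows section 5.1, that Tables 3 and 11 let a reader rescale, and that the complications in Tables 6 and 8, including aspiration pneumonitis, pneumothorax and arrhythmia, are shown for both arms. The last is a fair reason for a low rating. Allocation protects a comparison between arms, however, and Table 12 makes none. Rescaling works only if the reader knows how non-recipients were recorded.

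Three stronger readings are tempting, and the document does not support them.
- *Table 14, by delivery method, must contain recipients only and so must differ from Table 12.* Table 4 uses the same method columns and places non-receipt as a row inside them, so non-recipients may have a method recorded. The footnote to Table 14 also takes patients randomised to CPAP as its base.
- *Events before CPAP are certainly counted as CPAP harms.* Section 3.4 refers to an appendix, and SAP Appendix 1 defines no safety events. The definitions may lie in the protocol, which is not shown, and may require attribution to CPAP. In the SAP only the last, open-ended item carries a relatedness condition.
- *Usual care patients who received CPAP should be added to the harm table.* Section 3.4 measures these events in the treatment group only, so the plan provides no data for them, and a change of denominator does not reach them.

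**Conclusion.** The point holds in a limited form. Section 5.6 and Tables 12 and 13 summarise CPAP harms over all patients randomised to CPAP with a recorded outcome, although the stated aim is harm associated with CPAP and the SAP expects and records non-receipt.

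If non-recipients are recorded as event-free, device-specific rates are understated by the non-receipt share. With an assumed 5% to 15%, a true 10% prints as 9.5% to 8.5%. If their items are blank, there is no understatement. Both the share and the 10% rate are assumptions.

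On timing, the text supports only that the window may include time before randomisation and CPAP, so non-specific events may precede exposure. It does not show how many do, or that they are counted.

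Severity is minor. The tables are descriptive and single-arm, no test depends on them, and the primary analysis is unaffected.

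**What to change.** 1. In section 5.6 and Tables 12 to 14, make the denominator the CPAP-group patients who received any CPAP and have a recorded outcome. Recipients are the count in the first row of Table 11, and the complement within the CPAP group of the non-adherence definition in section 5.11.
2. In a footnote, give the number allocated to CPAP but untreated, with any events recorded in them. The all-allocated figures may be kept alongside.
3. Add a table note that the 24-hour window starts at the end of surgery, so pain, vomiting and haemodynamic instability may precede CPAP. Separate earlier from later events only if onset times were collected. Section 3.4 mentions presence or absence only, so a rule that counts events by onset should not be written in without checking this.

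The cost is a few lines of SAP wording, one changed denominator and two table notes. No new data are needed for the denominator, because receipt of CPAP is already recorded. The downside is that device-specific rates will look slightly less favourable.

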4.3 Sample size

The primary outcome is a composite endpoint of pneumonia, re-intubation, or death within 30 days of randomisation. The incidence of postoperative pneumonia in previous trials was 8.0% in the usual care group and 4.3% (relative risk reduction of 46%) in the treatment arm. However, the total number of patients included in these five trials was less than 600 patients. The incidence of postoperative pneumonia, admission to intensive care (a surrogate marker of re-intubation) and death in a large international cohort (n ~9000) was 11.7% for patients aged over 45 years [1]. In order to detect a reduction from 11.7% to 8.8% in the primary outcome measure (relative risk reduction of 25%), with 90% power, a type I error rate of 5%, and a loss to follow up rate of 4%, we would require a total sample size of 4800 patients (2400 per group). This sample size will allow us to detect a 26% relative risk reduction (7.7% vs. 5.7%) in the secondary outcome measure of mortality at one year after randomisation, with 80% power and a type I error rate of 5%. The sample size was calculated, using the *'power two proportions'* function in STATA 14.0 (StataCorp, College Station, USA).

5. Analysis Principles

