Table 13: Summary of 'other' safety outcomes with a prevalence of more than 1%

Other Adverse Events - no.(%)	CPAP (n=XXXX)
Total number of other adverse events	XXX (XX.X %)
Type of adverse event	
Other 1	XXX (XX.X %)
Other 2	XXX (XX.X %)
Other 3	XXX (XX.X %)
Other 4	XXX (XX.X %)
Other 5	XXX (XX.X %)

Table 14: Safety outcomes measures by CPAP delivery method

Adverse Events		CPAP ^a (n=XXXX)				
Adverse Events	Face mask (n=XXXX)	Helmet device (n=XXXX)	Nasal mask (n=XXXX)			
Patients with ≥ 1 adverse event	XX (XX.X %)	XX (XX.X %)	XX (XX.X %)			
Total number of adverse events	XXX	XXX	XXX			
Number of adverse events per patient						
0	XXX (XX.X %)	XXX (XX.X %)	XXX (XX.X %)			
1	XXX (XX.X %)	XXX (XX.X %)	XXX (XX.X %)			
2	XXX (XX.X %)	XXX (XX.X %)	XXX (XX.X %)			
3	XXX (XX.X %)	XXX (XX.X %)	XXX (XX.X %)			
4	XXX (XX.X %)	XXX (XX.X %)	XXX (XX.X %)			
Type of adverse event						
Interface intolerance due to excessive air leak	XXX (XX.X %)	XXX (XX.X %)	XXX (XX.X %)			
Pain	XXX (XX.X %)	XXX (XX.X %)	XXX (XX.X %)			
Cutaneous pressure area	XXX (XX.X %)	XXX (XX.X %)	XXX (XX.X %)			
Claustrophobia	XXX (XX.X %)	XXX (XX.X %)	XXX (XX.X %)			
Oronasal dryness	XXX (XX.X %)	XXX (XX.X %)	XXX (XX.X %)			
Hypercapnia	XXX (XX.X %)	XXX (XX.X %)	XXX (XX.X %)			
Haemodynamic instability	XXX (XX.X %)	XXX (XX.X %)	XXX (XX.X %)			
Vomiting	XXX (XX.X %)	XXX (XX.X %)	XXX (XX.X %)			
Aspiration of gastric contents	XXX (XX.X %)	XXX (XX.X %)	XXX (XX.X %)			
Other	XXX (XX.X%)	XXX (XX.X%)	XXX (XX.X%)			

^aXXX patients had missing data on CPAP method out of XXXX patients randomised to the CPAP group

ARISCAT	Number of patie analysis -	Summary measure		
	Usual Care (n=XXXX)	CPAP (n=XXXX)	Usual Care	СРАР
ARISCAT Score				
Mean (SD)				
Median (IQR)				
Components				
Age (years) - no. (%)				
≥50				
51-80				
> 80				
Percentage peripheral oxygen saturation (SpO ₂) - no. (%)				
≥ 96%				
91-95%				
≤90%				
Respiratory infection within the last month - no. (%)				
Preoperative anaemia (Hgb ≤10 g/dL) – no. (%)				
Surgical incision - no. (%)				
Upper abdominal				
Intrathoracic				
Peripheral				
Duration of surgery - no. (%)				
< 2 hours				
2-3 hours				
> 3 hours				
^a Emergency procedure - no. (%)				

Abbreviation: SD, standard deviation; IQR, interquartile range

^a All patients recruited in the trial were elective

Table 16: Pre-specified subgroup analyses for primary outcome

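### The 1% cut-off for naming 'other' CPAP harms uses all trial participants as denominator, although only the CPAP group is assessed, so it works as 2% of that group

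*SAP*

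**What the plan says.** Section 3.4 lists the safety outcomes and states that their presence or absence "will be measured within 24 hours of the end of surgery in patients in the treatment group only". Nine harms are named. The tenth entry is a residual category: "Other harm assessed as probably or definitely related to CPAP".

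Section 5.6 first gives the general rule: "Each safety outcome measured will be summarised for patients in the CPAP group by the number" and percentage. It then adds a rule for the residual category only. Types of 'other' "adverse events will be reported separately if prevalence is more than 1% across all participants in the trial".

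In Appendix 2, Table 13 is the shell for that separate listing. Its title is "Summary of 'other' safety outcomes with a prevalence of more than 1" per cent, with no indication of whom the percentage is taken over, and its only data column is the CPAP group. Tables 12 and 14 carry a single pooled 'Other' row, overall and by delivery method.

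On numbers, section 4.2 says "Participants will be centrally allocated to treatment groups (1:1"), and section 4.3 says "we would require a total sample size of 4800 patients (2400 per group").

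**The concern.** The two halves of the prevalence come from different populations. The events can arise only among CPAP patients, because nobody else is assessed for them, yet the count is compared with 1% of both arms together. Equal allocation then doubles the cut-off as seen from the CPAP group.

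The purpose of listing 'other' events by type is to bring out harms that were not foreseen when the named list was drawn up. By definition they have already been judged probably or definitely related to CPAP. A threshold twice its nominal size makes it less likely that such a harm is identified.

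The table shell does not help. With one CPAP column and a title that gives no denominator, the absence of an event type from Table 13 could be read as meaning that it occurred in no more than 1% of CPAP patients. Followed literally, section 5.6 supports only the statement that it occurred in no more than 2%.

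**Working it through.** **Inputs.** Planned total 4800, 2400 per group (section 4.3); allocation 1:1 (section 4.2); assessment in the CPAP group only (section 3.4); threshold more than 1% of all participants (section 5.6). I take prevalence to count patients, not episodes.

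**Step 1: the plan's own sample size.** It fixes both denominators, so it is checked first. Section 4.3 gives 11.7% against 8.8%, 90% power, type I error 5% (two-sided by section 5.1) and 4% loss. With pooled variance under the null and no continuity correction,

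n per arm = [1.960 × √(2 × 0.1025 × 0.8975) + 1.282 × √(0.117 × 0.883 + 0.088 × 0.912)]² / (0.117 − 0.088)² = 2297.

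Allowing for 4% loss, 2297 / 0.96 = 2393 per arm, or 4786 in total. The stated 4800 is reproduced, allowing for rounding up.

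**Step 2: the cut-off as written.** 0.01 × 4800 = 48. More than 1% means at least 49 patients, all of whom must be CPAP patients. The largest count that is not named is 48/2400 = 2.00%; the smallest that is named is 49/2400 = 2.04%.

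**Step 3: the cut-off on the CPAP group.** 0.01 × 2400 = 24. At least 25 patients are needed, and 25/2400 = 1.04%.

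**Step 4: the gap.** Types seen in 25 to 48 CPAP patients (1.04% to 2.00%) would be named under the second rule but not under the first.

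**Step 5: dependence on reaching 4800.** As a share of the CPAP group, the written cut-off is 1% × (1 + usual-care number / CPAP number), which is 2% whenever the arms are equal. If, for illustration, the 4% loss in section 4.3 also applied to the safety data, the numbers would be 4608 and 2304. The largest unnamed count is then 46, and 46/2304 is again 2.0%.

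**Step 6: chance that a type is named**, from the exact binomial tail with n = 2400. The true rates are assumed; the SAP gives none.

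| True rate in CPAP group | As written (49 or more) | CPAP denominator (25 or more) |
|---|---|---|
| 1.25% | 0.1% | 84.4% |
| 1.5% | 2.2% | 97.8% |
| 1.75% | 15.6% | 99.8% |
| 2.0% | 46.2% | over 99.9% |
| 2.5% | 93.7% | over 99.9% |

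**The case against.** The strongest reply is that no event is lost. Section 5.6 summarises every safety outcome in the CPAP group without any threshold, and the residual category is itself one of those outcomes. Each such event enters the 'Other' row, the count of patients with at least one event and the total in Table 12, and the 'Other' row in Table 14. The nine named harms are shown at any frequency. This stands in full. A reader might infer that CPAP harms affecting up to 2% of the group go unreported; the SAP does not support that. What is lost is the type, not the count.

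A second reply is that section 5.7 tabulates a long list of 30-day complications in both arms with no frequency threshold, including pneumothorax, bronchospasm and arrhythmia. A harm on that list would be named anyway. This narrows the practical effect. It does not remove it, because an event outside that list would fall into another unspecified category there.

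A third is that the analyst may read the sentence as meaning all CPAP participants, as the single column of Table 13 suggests. That is possible, but the sentence refers to the whole trial, while the sentence opening the same section names the CPAP group. If the narrower meaning was intended, the wording still needs correcting.

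One might also object that the CPAP group contains patients who never received CPAP, so that even its own denominator is too wide, and ask for a further column. That is a preference. Reporting by randomised group fits section 5.1, and Tables 3 and 11 already give the numbers without and with CPAP.

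**Conclusion.** The denominator in section 5.6 does not match the population assessed under section 3.4, and nothing elsewhere in the SAP repairs it. Applied literally, the rule doubles the threshold for naming an unforeseen CPAP-related harm, from just over 1% to just over 2% of the CPAP group.

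The factor of two rests on equal arms. The counts of 25 and 49 rest on the planned 4800. Nothing in the SAP shows that an unlisted event type in the affected range is expected, so the effect may turn out to be nil.

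Severity is minor. This is a display rule for descriptive safety tables; no test, estimate, or primary or secondary outcome depends on it.

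**What to change.** In section 5.6, replace the trial-wide denominator so that a type of 'other' adverse event is listed separately when it occurs in more than 1% of patients in the CPAP group with a recorded safety outcome. Repeat that denominator in the title of Table 13.

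The cost is one sentence in the text, a few words in a table title and possibly some extra rows in Table 13. No new data and no change to any analysis are needed.
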